Specify the projected date of completion of the study.

Section 2: Participating Site Specifications

2.1. Where will the research project be conducted? (Check all that apply)

 VA Inpatient Setting	 VA Outpatient Clinic/Office
 VA Laboratories	 Subject Homes
 University of Pennsylvania	 Community Based Outpatient Clinics (CBOCs)
 Other (Specify): 	

2.2. If research is conducted at a non-VA site, please specify where and how much of the project will be conducted at that location. This project will remotely track veterans' physical activity with the use of a wearable device.

Section 3: Introduction

3.1. Provide scientific background and rationale for study. Including summary of gaps in current knowledge, relevant data, and how the study will add to existing knowledge. Over 80% of veterans have at least two risk factors for cardiovascular disease (CVD). Regular physical activity is associated with reduced risk for CVD, but less than half of veterans achieve enough physical activity to obtain these benefits. Digital health approaches that use engagement strategies such as gamification are commonly found within workplace wellness programs and mobile applications, but the evidence is limited. In 2015, the Veterans Affairs Evidence-Based Program published a systematic review which found only 14 trials on the use of wearable device technology with none that enrolled veterans for the purpose of testing how these devices could augment physical activity. Our prior work has demonstrated that wearables may be appropriate for monitoring health behaviors, but they alone they do not drive behavior change.

Social incentives or those influences that impact individuals to adjust their behaviors based on social ties and connections have been demonstrated in retrospective studies to influence behavior but have not been well examined prospectively. Insights from behavioral economics can be used to design gamification interventions to enhance social incentives such as the support, competition, or collaboration but the optimal design to increase physical activity is unknown. This study will use behavioral economics frameworks to design and test a social incentive-based gamification intervention with and without financial incentives to increase physical activity among overweight and obese veterans. We will test whether this intervention can be conducted remotely, thereby reducing participant burden of coming in for an in-person visit and creating a more scalable intervention design. Specifically, we will test the ability of using wearable devices with social and financial incentive-based interventions to augment physical activity as measured by change in mean daily step counts which will be tracked by a wearable activity tracker.

Section 4: Objectives Section

4.1. Describe the study's purpose, specific aims, or objectives.

The objective of this study is to use a randomized, controlled trial to test the effectiveness using a remotely-monitored social incentive-based gamification intervention with and without financial incentives to increase physical activity among overweight and obese veterans. All participants will use wearable devices to establish a baseline step count and monitor their physical activity during the study.

Primary outcome: The primary outcome is change in mean daily steps from baseline to the weeks 5 to 12 of the intervention period (which excludes the 4-week ramp-up phase).

Secondary outcomes: Secondary outcomes include change in mean daily steps from baseline to the 8-week follow-up period, Proportion of participant-days achieving step goals during the intervention and follow-up periods.

Exploratory outcomes: We will explore how participant characteristics and behaviors are associated with strong or poor physical activity performance.

4.2. **State the hypotheses to be tested.**

Hypothesis: The combination of social and financial incentives will lead to greatest increase in mean step counts from baseline.

Section 5: Study Procedures

5.1. **Study Design**

5.1.1. **Describe in detail the experimental design, i.e. from recruitment procedures to study closure.**

Design: This is a three-arm randomized, controlled trial with a 12-week intervention period and 8-week follow-up period. The study will be conducted using Way to Health (WTH), a research information technology platform at the University of Pennsylvania that has been used previously at the CMCVAMC for a behavioral study.

Study duration: This study is anticipated to take up to 2 years to complete and includes a 12-week intervention period and 8-week follow-up period.

Target population: Veterans, age 18 years or older, who received care at the CMCVAMC and have a body mass index of 25 or greater.

Accrual: This study has been powered for two phases of hypothesis testing. In the first phase, we will compare each of the two intervention arms to control. We estimate that a sample of 180 participants allocated in a 1:1:1 distribution, will ensure at least 80% power to detect a 900-step difference between each intervention arm and control, with a standard deviation of 1500 steps. This calculation assumes a 10% missing data rate and a conservative Bonferroni adjustment of the type I error rate with a 2-sided alpha of 0.025. In the second phase, we will compare successful intervention arms to each other. We expect that the magnitude of difference between intervention arms will be less than that of successful intervention arms compared to control. For this second phase of analyses will use a conservative Bonferroni adjustment of the type I error rate with a 2-sided alpha of 0.017 to adjust for up to 3 comparisons. In 2012, more than 57,500 veterans enrolled for care at CMCVAMC and comprised nearly 463,000 visits. Since 70% of veterans are overweight or obese, nearly 40,000 veterans may be eligible for this study. Based on this data and prior studies, we estimate that we can fill the study within 6 months. We will plan to oversample women and minorities in the recruitment process.

Interventions:

In order to minimize cost, time and travel for Veterans and to make study the least burdensome as possible, recruitment and enrollment will be completed remotely. Veterans will be asked to verify their identity using their name and age. Participants will be enrolled remotely using a standardized eligibility survey which will be conducted over the phone. Once deemed eligible and oral consent is obtained, participants will be asked to complete a telephone survey to obtain demographic data, activity data and information on use of technology. Participants will be told to wear the activity tracking device during day and night to get accustomed to it during a 2-week run-in period. Data collected from this time will be used to estimate a baseline step count using methods from prior work by using data from the second week (days 8 to 14), ignoring values less than 1000 steps (since evidence suggests these values are unlikely to represent actual activity). Participants without at least 4 days of data will be called to inquire if there are any issues with using the device and the period will be extended until at least 4 days of data are available to estimate a baseline step count.

Participants that have been confirmed by the study team to have an appropriate baseline step count will be called and asked to select a step goal increase as follows:

Goal Setting: Each participant will be asked to choose a step goal increase that is between 33% and 50% higher than their baseline (each step goal will be rounded up to the nearest hundred). A participant may also select to choose another goal as long as it is at least 1500 steps greater than his or her baseline.

Randomization: Participants are considered ready to be randomized once they have completed all surveys, established a baseline step count, and selected a step goal increase. Participants will be stratified on baseline step count (less than 5000 steps, 5001 to 7500 steps, or more than 7500 steps). Participants will then be randomly assigned within their strata in blocks of three. Participants in all arms will be asked to complete end of study surveys at 20 weeks on their experience in the study. The interventions within each arm are as follows:

Arm 1: Control

Participants in this arm will receive no other interventions during the 20-study.

Arm 2: Social incentive-based gamification intervention

Participants randomized to Arm 2 will play a game designed to leverage insights from behavioral economics and to enhance *supportive* social incentives.

At the beginning of each week the participant receives 70 points (10 for each day that week). If the participant does not achieve their step goal, they lose 10 points from their balance. This leverages loss aversion, which has been demonstrated to motivate behavior change more effectively with losses than gains. At the end of each week if the participant has at least 40 points, he or she will move up a level (levels from lowest to highest: blue, bronze, silver, gold, platinum). If not, participants will drop a level. All participants begin at the silver level. Each week, participants get a fresh set of 70 points on Monday.

Each participant will identify a family member or friend as a support sponsor. This sponsor will be encouraged to support the participant in their progress during the study. A weekly report will be sent by email to the sponsor with the participant's performance (e.g., step goal, average step count for that week, points and level).

Arm 3: Supportive social incentive intervention plus financial incentive

Participants randomized to Arm 3 will play the same game as in Arm 2 but will also have \$120 placed in a virtual account. Each week if the participant reaches a higher level, having at least 40 points, they will keep the money in the account. If not, then \$10 will be deducted. This will leverage prior work demonstrating that loss framed financial incentives can be used to increase physical activity. A participant in Arm 3 must complete the full course of the study intervention timeline to obtain any of this amount (up to \$120).

5.1.2. What research methods will be used in the project? *Check all that apply.*

 Surveys/Questionnaires	 Interviews	 Audio Taping
 Behavioral Observations	 Chart Reviews	 Video Taping
 Focus Groups	 Randomization	 Double-Blind
 Control Group	 Placebo	 Withhold/Delay Treatment
 Specimen Collection	 Deception	 Telephone Survey
 Other (Describe) Physical activity tracking via a wearable device.		

5.1.3. Provide description of the study population (delineate all categories of subjects – male, female, inpatients, outpatients, providers, family members, employees, etc.). Include anticipated initial enrollment numbers (and number of subjects anticipated to complete all aspects of the protocol).

The study population will include 180 participants total: 1) adults age 18 years or older; 2) interest in participating in a 20-week study using wearable devices to track step counts and increase physical activity; 3) body mass index of 25 or greater; 4) Smartphone or tablet compatible with application for the wearable activity tracking device.

5.1.4. **As applicable, provide rationale and information on any added protections and safeguards for vulnerable populations (children, prisoners, pregnant women, physically or mentally-disabled persons, and economically or educationally disadvantaged persons).**

This will not include children or prisoners. For other vulnerable populations, this study will only include subjects wishing to participate by wearing a physical activity tracking device. Those individuals with physical disability which prevents them from wearing the device or for its proper tracking will not be included in the study.

5.1.5. Does this project target a specific race or ethnic group as subjects? **NOT APPLICABLE**
If yes, check all that apply.

Race

American Indian or Alaska Native
 Asian
 Black or African American
 Native Hawaiian or other Pacific Islander
 White
 Other

Ethnicity

Hispanic or Latino
 Not Hispanic or Latino

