### **4. Imputation plan**

- a. Change in mean daily steps
  - i. Model driven approach to run 5 imputations for any missing values or values < 1000 steps
  - ii. Covariates include: study arm, week of study, calendar month, baseline step count, age, gender, race/ethnicity, education, marital status, annual household income, military service period, and BMI

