### **6. Adjusted changes in outcome measures (imputed model is primary; non-imputed is secondary)**

- a. Use generalized linear mixed models (GLIMMIX) with identity link for mean change in daily steps during weeks 5-12 and weeks 13-20.
  - i. Adjusted for baseline steps, calendar month, study arm, participant random effect
- b. Use generalized linear mixed models (GLIMMIX) with logit link (logistic model) for proportion of days achieving step goal during weeks 5-12 and weeks 13-20
  - i. Adjusted for baseline steps, calendar month, study arm, participant random effect
  - ii. Use 1000 bootstrapped samples to find adjusted changes in percentage points with 95% confidence intervals for proportion of days achieving step goals

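### The first week of run-in step data is collected before randomization but never analysed; adding its mean as a second covariate is a near-free precision gain of uncertain size

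*Protocol*

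**What the plan says.** Protocol 5.1.1 (Interventions) describes the run-in: "Participants will be told to wear the activity tracking device during day and night to get accustomed to it during a 2-week run-in period". The baseline is then estimated "by using data from the second week (days 8 to 14), ignoring values less than 1000 steps". If fewer than four days are available, the participant is called and the period is extended until there are four. No minimum is set for days 1-7. A baseline must be in place before a participant is ready for randomization, so days 1-7 are pre-randomization data.

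Each model carries one step covariate:

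- Protocol 9.2 adjusts the primary mixed model for baseline step count and time.
- SAP 6.a.i (steps) and 6.b.i (goal attainment) share one specification: "Adjusted for baseline steps, calendar month, study arm, participant random effect".
- SAP 4.a.ii, imputation: "Covariates include: study arm, week of study, calendar month, baseline step count", followed by demographic variables and BMI.

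Neither document gives days 1-7 an analytic role. The power statement (Protocol 5.1.1, repeated in 9.1) claims "at least 80% power to detect a 900-step difference between each intervention arm and control, with a standard deviation of 1500 steps", from "a sample of 180 participants allocated in a 1:1:1 distribution". It adds "This calculation assumes a 10% missing data rate" and "a conservative Bonferroni adjustment of the type I error rate with a 2-sided alpha of 0.025".

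**The concern.** A mean of four to seven days measures a person's usual activity with error. Adjusting for it leaves some predictable between-person variation in the residual of the weeks 5-12 outcome. Days 1-7 are a second measurement of the same quantity, and the trial already has them for those who wore the device.

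The run-in's stated purpose, getting used to the device, is a reason to keep week 1 out of the baseline. It is not a reason to keep week 1 out of the model. A novelty effect before randomization is balanced across arms in expectation: a common shift goes into the intercept, and extra noise only weakens the covariate.

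At stake is precision, not validity. The design has little spare power against control. The protocol also expects a smaller difference between the two intervention arms, which it tests at 0.017.

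**Working it through.** **1. The plan's own figure.** Inputs from Protocol 5.1.1: difference 900, SD 1500, two-sided alpha 0.025, power 80%, 10% missing.

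- n per arm = 2 × (2.2414 + 0.8416)² × (1500/900)² = 52.8, so 53.
- 53/0.90 = 58.9, so 59 per arm and 177 in total, against 180 stated. The figure reproduces.
- With 60 × 0.90 = 54 per arm, SE = 1500 × √(2/54) = 288.7 and 900/288.7 = 3.118. Power = Φ(3.118 − 2.241) = 81.0%; the noncentral t on 106 df gives 79.9%.

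**2. Gain in terms of one unknown.** Let p be the partial correlation of the week-1 mean with the outcome, given the baseline. If 1500 is the residual SD under the planned model, the new residual SD is 1500 × √(1 − p²). Power by the normal formula:

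| p | Power |
|---|---|
| 0 | 81.0% |
| 0.1 | 81.4% |
| 0.2 | 82.7% |
| 0.3 | 84.8% |
| 0.4 | 87.7% |

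**3. Gain from assumed variance components.** The documents give no between-person SD (B), day-to-day SD (D) or week-to-week correlation, so these are assumptions. Let τ be the SD of extra person-level noise in week 1. With independent days:

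- Error variance of the baseline mean: v2 = D²/k2, for k2 days.
- Error variance of the week-1 mean: v1 = D²/k1 + τ², for k1 days.
- Variance of usual activity given the baseline: 1/(1/B² + 1/v2).
- Given both means: 1/(1/B² + 1/v2 + 1/v1).
- Variance cut = the difference of these two, divided by 1500².

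Worked cell: B = D = 2000, seven days in each week.

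- τ = 0: 4,000,000/8 = 500,000 falls to 4,000,000/15 = 266,667. The cut is 233,333/2,250,000 = 10.4% and the residual SD is 1420. Power is 85.4% by the normal formula and 84.4% by noncentral t.
- τ = 1000: v1 = 571,429 + 1,000,000 = 1,571,429, and 500,000 falls to 379,310. The cut is 5.4%, the SD 1459, and power 83.2% and 82.3% respectively.

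Grid: B 2000-2500, D 1500-2500, τ 0-1500, day-to-day autocorrelation 0-0.2 (which inflates v1 and v2), six usable week-1 days. Power is by noncentral t with 54 per arm, starting from 79.9%.

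| Baseline days | Variance cut | Median cut | Power range | Power at median |
|---|---|---|---|---|
| 7 | 1-20% | about 8% | about 81-88% | about 83% |
| 6 | 2-23% | about 10% | about 81-90% | about 84% |
| 4 for everyone (extreme) | 3-36% | about 16% | about 81-95% | about 87% |

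**4. Drift.** The grid treats usual activity as stable over the run-in. With weekly person-level drift of SD 1000-1500, week-to-week correlation 0.8-0.95 and week-1 noise 500-1000 (also assumptions), the cut is about 2-6% and power about 81-83%.

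**5. Bias.** A simulated ANCOVA with an 800-step week-1 novelty shift returned 900 for a true effect of 900. Rejection under the null was 2.7% without and 2.9% with the covariate, against a nominal 2.5%. Its components (B and D both 2500) were favourable, so its precision gain is not used here.

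**6. Cost if week 1 is uninformative.** One degree of freedom moves power from 79.93% to 79.92%. A direct check with a useless covariate gave 80.3% and 80.0%, about 0.3 points.

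**The case against.** The strongest reply is that nothing is wrong. The sample size reproduces, the primary model already adjusts for baseline, and nothing is biased or unanalysable. That stands: this is an efficiency gain and not a defect.

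Four stronger readings are tempting, and the documents do not support them.

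- **A large typical gain.** A reader might take a 15% variance cut as typical, equivalent to 180/0.85 = 212 participants. The documents contain no variance components, the medians above are 8-10%, and drift lowers them.
- **Week-1 data on everyone.** Wear is asked of all participants, but the four-day minimum applies only to the baseline. Some may have few or no valid days in week 1.
- **A trial at exactly 80% power.** The protocol does not say whether 1500 is the SD of the change or a residual SD. If it is the SD of the change, the planned adjustment may already give about 81-90% with a seven-day baseline, and the further gain is about 1 to 9 points.
- **A demonstrated gain on every endpoint.** Only the linear primary contrast against control was calculated. The logit model, weeks 13-20 and the comparison between intervention arms were not.

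It is also fair to object that the change is not wholly free. Protocol 9.2 names the covariates too, and rules are needed for missing week-1 data and an extended run-in.

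**Conclusion.** The point holds as an optional improvement. Days 1-7 precede randomization, no planned analysis uses them, and their mean is an unbiased addition to models that now rest on a 4-7 day baseline.

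The direction of the gain is well founded; its size is not known. With 6-7 baseline days the variance cut is about 1-23% (median about 8-10%), and primary power moves from about 80% to about 81-90% (centre about 83-84%). This rests on the assumed components, on 54 evaluable per arm, on 1500 being a residual SD, and on a comparison of person-level means standing in for the mixed model. Drift between weeks would make the gain smaller. Secondary outcomes should benefit in the same direction, by an amount not quantified. The loss if week 1 adds nothing is negligible.

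**What to change.** Before arms are unblinded (Protocol 5.6.1.6 keeps them coded until analysis is complete):

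1. Add the mean of valid days 1-7 (values of 1000 steps or more) as a covariate next to baseline steps in SAP 6.a.i and 6.b.i.
2. Add it to the imputation covariates in SAP 4.a.ii.
3. Put matching text in Protocol 9.2.
4. If a participant has no valid day in days 1-7, set the covariate to the baseline value and include a missing indicator.
5. If the run-in is extended, the covariate still uses days 1-7 only and excludes any day counted in the baseline.

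Leave the baseline definition, strata, step goals and change-score outcome unchanged.

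The cost is a few lines in two documents and one model degree of freedom, or two with the indicator. No new data, contacts or participants are needed.

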5.4.5. **Inclusion/Exclusion Criteria: Describe the criteria that determine who will be included in or excluded from the study.**

5.4.5.1. **Inclusion Criteria**

1) Age 18 years or older; 2) interest in participating in a 20-week study using wearable devices to track step counts and increase physical activity; 3) body mass index of 25 or greater; 4) Smartphone or tablet compatible with application for the wearable activity tracking device.

5.4.5.2. **Exclusion Criteria**

1) Conditions that would make participation infeasible such as inability to provide informed consent, illiteracy or inability to speak, read, and write English; 2) conditions that would make participation unsafe such as pregnancy or being told by a physician not to exercise; 3) already enrolled in another study targeting physical activity; 4) any other medical conditions or reasons he or she is unable to participate in a physical activity study for 20 weeks.

5.5. **Withdrawal of Subjects**

5.5.1. **Describe how a subject can withdraw from the study.**
Subjects may withdraw at any point by informing the study team either by written mail or by phone.

5.5.2. **Describe any anticipated circumstances under which subjects will be withdrawn from the research without their consent.**
None.

5.5.3. **Describe the consequences of a subject's decision to withdraw from the research and the procedures for orderly termination of participation by the subject (e.g., the subject contacting the investigator for an end-of-study visit).**
Patients choosing to withdraw early in the study will not receive the total compensation as described above. Patients are free to, at any time, contact the study team to be removed from the study.

5.6. **Potential Risk/Benefit Analysis**

5.6.1. **Potential Study Risks**

5.6.1.1. **Describe and assess all of the following risks that may be associated with the research:**

5.6.1.2. **Physical**

To minimize the chance for serious and unexpected adverse events, study participants will be screened through exclusion criteria for any health conditions that may be exacerbated by participating in a physical activity study. The program will use a gradual increase in physical activity during the first month that should pose little health risk to participants. Participants are given guidance on when to seek medical attention and a reporting protocol is in place to capture any changes in symptoms with physical activity.

5.6.1.3. **Psychological:** Not applicable.

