5.6.1.4. **Social/Economic**

Each participant in the two intervention arms will identify a support partner (friend or family member) who will receive weekly updates by email on their progress in the game. That support partner will be encouraged to help the participant to achieve their goals.

5.6.1.5. **Legal:** Not applicable.

5.6.1.6. **Loss of Confidentiality**

A potential risk of this study is a breach of participant confidentiality. We will minimize this risk by using secure data methods as described previously. Names and addresses will be stored in encrypted databases. These data will be viewable only by the respective participants and the study coordinator. All other members of the research team will be able to view only participant ID numbers. There will be no functionality in the web application to export a dataset with identifiable information. Even the study arms will be identified by code letters until both the statistician and PI agree that analysis is complete.

5.6.1.7. **Other, e.g. radiation, placebo, washout of medications:** Not applicable

5.6.1.8. **Assess the likelihood and seriousness of such risks.:** Not applicable

5.6.2. **Include a description of how anticipated risk will be minimized and include an analysis of risk vs. potential benefit.**

Anticipated risks of this study should be minimal and the risk/benefit ratio is very favorable. To minimize the chance for serious and unexpected adverse events, study participants will be screened through exclusion criteria for any health conditions that may be exacerbated by participating in this study. We have previously outlined the procedures that will be used to prevent a breach of participant data.

5.6.3. **Potential Study Benefits**

5.6.3.1. **Indicate potential benefits to be gained by the individual subjects, as well as benefit(s) that may accrue to society in general as a result of the planned work. If the subject will not receive any direct benefit, this fact must be stated here and in the consent form.**

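### A single fixed block of three in an open three-arm trial makes every third assignment in a stratum predictable; withheld, randomly varying block sizes remove most of that certainty at almost no cost

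*Protocol*

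**What the plan says.** Protocol 5.1.1 (Design, Accrual, Randomization) describes three arms at 1:1:1 with 180 participants in total, stratified into three bands of baseline steps. "Participants will then be randomly assigned within their strata in blocks of three". No other block size is given, and the SAP does not discuss randomization.

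The order of events is set in the same section. The baseline is estimated "using data from the second week (days 8 to 14), ignoring values less than 1000 steps", and the run-in is extended until at least four days of data exist. The study team confirms the baseline and calls the participant to choose a goal: "Each participant will be asked to choose a step goal increase that is between 33% and 50% higher than their baseline". A different goal is allowed if it is at least 1,500 steps above baseline. Only then does randomization follow: "Participants are considered ready to be randomized once they have completed all surveys, established a baseline step count, and selected a step goal increase".

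The arms look different to participants and to those running them: control, a game with a sponsor who receives weekly emails, or the same game plus a $120 virtual account. The double-blind box in 5.1.2 is not ticked. The one masking statement is in 5.6.1.6: "Even the study arms will be identified by code letters until both the statistician and PI agree that analysis is complete".

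**The concern.** With three arms at equal allocation, three is the smallest possible block and therefore the most predictable. If the person arranging or making the goal call can guess the next arm, the order in which participants enter, or the way the call is conducted, can shift, knowingly or not.

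The goal chosen on that call defines success for the secondary outcome in Protocol 4.1: "Proportion of participant-days achieving step goals during the intervention and follow-up periods". The SAP's logistic model for that outcome (6.b.i) is "Adjusted for baseline steps, calendar month, study arm, participant random effect", so it accounts for baseline but not for the goal. A systematic difference between arms in goals chosen would pass into that comparison. No bias in step counts is claimed.

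**Working it through.** **The plan's own figure first.** Inputs from Protocol 5.1.1 and 9.1: difference 900, SD 1,500, two-sided alpha 0.025, power 80%, 10% missing.
- n per arm = 2(2.241 + 0.842)² × (1500/900)² = 52.8, so 53. Then 53/0.9 = 58.9, so 59 per arm and 177 in total, against 180 planned.
- With 54 evaluable per arm: 900/(1500√(2/54)) − 2.241 = 0.876, which gives power of 81.0% (79.9% by noncentral t). The stated 80% is reproduced.

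**Fixed blocks of three, all earlier assignments in the stratum known.**
- Certain: the third place in each block, 1/3 = 33.3%, or 60 of 180.
- Correct guesses: (1/3 + 1/2 + 1)/3 = 61.1%.

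**Fixed blocks of three, each earlier assignment known with probability p, block position known.**
- Certain: p²/3.
- Correct: [1/3 + (p/2 + (1−p)/3) + (p² + p(1−p) + (1−p)²/3)]/3.

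**Random sizes 3, 6 and 9, equally likely and withheld.** Lists of 60 per stratum were simulated, with an observer who updates optimally on what has been seen. The values of p are assumptions; the documents give none.

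| p | Fixed 3: certain | Fixed 3: correct | 3/6/9: certain | 3/6/9: correct |
|---|---|---|---|---|
| 1 | 33.3% | 61.1% | about 3.5% | 55% |
| 0.75 | 18.8% | 52.1% | about 0.4% | 47% |
| 0.50 | 8.3% | 44.4% | 0.02% | 42% |
| 0.25 | 2.1% | 38.2% | 0% | 38% |

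An observer who sees the same share of assignments but cannot count the unseen enrolments is never certain under either scheme. Correct guesses are then about 52%, 44% and 38% with fixed blocks, and 46%, 41% and 37% with 3/6/9.

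**If each block's size is known.** The expected number of certain places is 1 in a block of 3, 1.2 in a block of 6 and 1.286 in a block of 9.
- Sizes 3/6/9: (1 + 1.2 + 1.286)/18 = 19.4% certain.
- Sizes 3/6: (1 + 1.2)/9 = 24.4%.
- A single fixed block of 6: 1.2/6 = 20.0%.

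Most of the gain therefore depends on withholding the sizes.

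**Balance.** In simulated trials of 180 over three equally likely strata:

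| Block sizes | Mean largest-minus-smallest arm | 95th percentile |
|---|---|---|
| Fixed 3 | 1.2 | 2 |
| 3/6 | 1.6 | 3 |
| 3/6/9 | 1.9 | 4 |

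With 3/6/9, arms within a stratum differ by 2 or more in 20% of strata and by 3 in 2%; with fixed blocks the limit is 1. For two arms of 57 and 63, with 10% missing: 900/(1500√(1/51.3 + 1/56.7)) − 2.241 = 0.872, which gives power of 80.9%.

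**Room in the goal.** At a baseline of 5,000, 5,000 × 1.33 = 6,650, rounded up to 6,700, and 5,000 × 1.5 = 7,500. The alternative option allows 5,000 + 1,500 = 6,500, with no stated upper limit.

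**The case against.** The strongest reply is that varying the block size is the lesser part of the remedy. If earlier assignments by stratum are withheld, guessing falls to 33% under fixed blocks too. If they are not, correct guesses fall only from 61% to 55%, and by less with partial knowledge. An observer who cannot count unseen enrolments is never certain under either scheme. This stands, and it is why withholding comes first in importance.

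Second, the knowledge is assumed. Protocol 5.6.1.6 restricts team members other than the coordinator to ID numbers and codes the arms by letter, and the trial runs on an automated platform. The text under Section 6 on who conducts the research was not available, so nothing can be said about who allocates. This also stands, although the code letters serve the analysis and are not described as hiding the next assignment.

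Third, the room for influence is small. Consent and eligibility precede the run-in, and the stratum is unknown until the baseline is set. The baseline rule is fixed and the participant chooses the goal. On "Describe any anticipated circumstances under which subjects will be withdrawn from the research without their consent", Protocol 5.5.2 answers that there are none. What remains is mainly the timing and conduct of the goal call. That limits the importance of the point without removing it.

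**Conclusion.** The point holds as a low-cost improvement to consider. One fixed block size equal to the number of arms makes a third of assignments certain to anyone who knows the block size and all earlier assignments in the stratum. Withheld random sizes of 3, 6 and 9 cut that to about 4%, removing roughly nine in ten of the certain assignments, but lower guessing only modestly.

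The size of the problem in practice depends on how much staff know, which the documents do not state. This is a vulnerability affecting chiefly the goal-based secondary outcome; bias has not been shown, and the primary outcome is not put in question.

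**What to change.** In Protocol 5.1.1, replace the fixed block with permuted blocks of randomly varying size, for example 3, 6 and 9, within the same three strata. State that the sizes, the sequence and earlier assignments by stratum are kept from staff who confirm baselines or make goal calls. State also that each assignment is released only after the baseline and goal are recorded, which keeps the order the protocol already sets. If concealment is already in place, record it.

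The cost is one or two sentences and a different list, assuming the randomization system supports varying blocks; the available text does not say which system is used. Balance loosens slightly, as shown above, with negligible effect on power. Sizes 3 and 6 alone are a milder choice: about 9% certain and 58% correct in the worst case, with a mean arm difference of 1.6.
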